However, as aforementioned in the Introduction (section 2), the enrollment phase and all MBT testing (incl. Day1, Week 24 and Week 48 visits) for the aforementioned BMS sponsored studies has been completed. The data is still being assessed by BMS and the respective databases are planned to be made available to Exalenz between July and November 2021, after their respective data lock and release from BMS.

The initially planned sample size of 250 subjects, per statistical section in the companion protocol, was not reached for multiple reasons:

- The MBT testing as part of the BMS studies, was an opt in substudy, requiring an additional consent process. Subjects enrolled to the BMS studies were reluctant to add an additional investigational test to their study schedule.
- The COVID-19 outbreak further complicated the enrollment and especially the follow up testing of already enrolled subjects, as visits were more and more conducted remotely and any breath testing was avoided during in person visits.

Since the actual final sample size of subjects with valid MBT results at baseline and post-treatment phase, across both BMS studies, is expected to be lower than 80, the statistical analyses for the study will be descriptive by nature. No formal statistical testing will be performed. Nominal p-values from statistical tests will be reported for supplementary information.

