In order to show the ability of the MBT to measure the effect of BMS-986036 treatment on the metabolic capacity of the liver after Week 24 and Week 48 visits, as compared to changes in placebo treated subjects, the primary endpoint will be analyzed using a responder analysis, where any increase of MBT value will be considered as a response while a same value or a decrease of the MBT value will be considered as non-response.

The primary analysis will be conducted on the mEA set, with the PDR_{peak} and cPDR₃₀ responder rate of Week 24 and Week 48 of data from both BMS' studies.

Individual analyses for each cohort separately will also be reported.

8.4.2 *Secondary Endpoints*

8.4.2.1 *Prognostic Value of MBT in Overall Event-Free Survival*

In order to assess the prognostic value of MBT in prediction of liver disease deterioration (reported as liver-related clinical outcome events), the endpoint measures will be point estimates of Cox Regression's Hazard Ratio for classifying Subjects into risk groups for clinical deterioration with respective exact two-sided 95% confidence intervals in the placebo and treatment arms as determined by MBT. The MBT parameter to be used to predict liver-related clinical outcome events is PDR_{peak}. Any PDR_{peak} value of less or equal to 20 %/h (see **Appendix A** for detailed description of parameter calculation) will be considered as 'high risk' and any value above that threshold will be considered as 'lesser risk' (additional cut-off values may be explored). The dichotomic MBT result will be tested for significance using the Cox proportional hazards regression model with site and randomized arm as covariates. If the randomized arm factor is found non-significant (i.e. p-value > 0.05), then this factor will not be a covariate for the main analysis to be performed. If the randomized arm factor is found statistically significant (i.e. p-value ≤ 0.05), then the main analysis will be performed keeping this factor as a covariate (to 'adjust' the analysis for treatment).

The time-to-first event will be derived as the number of days between the Day 1 MBT test and the date when the first event occurs or when a subject is censored (i.e., event/censored date minus

Meridian Bioscience Israel Ltd.	Last update: May 05, 2021

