SAP for Protocol BMS-EX-0118: Companion protocol for the ¹³C-Methacetin Breath Test (MBT) for use in Bristol-Myers Squibb phase 2b studies for BMS-986036 (PEG-FGF21), under Protocols MB130-068 and MB130-069	Document Version: 1.0
Document Nº: CSD00114	Page 17 of 21

Day 1 MBT date plus 1). Subjects will be censored at their last study visit for the following reasons:

- If a subject discontinues the study prior to the end of the study without experiencing an event
- If a subject reaches the Final Treatment visit without experiencing an event

Survival analysis will be conducted using the Cox proportional hazard model. The model summary will include the number of subjects in the model, and a table with each covariate in a separate line specifying the coefficient's value, Hazard Ratio, Hazard Ratio 95% Confidence Interval and p-value. In addition, a Kaplan-Meier plot for event-free survival will be presented, stratified by MBT parameter along with the MBT parameter log-rank p-value. Additionally, a crosstab table of MBT parameter and events will be presented.

8.4.2.2 Correlations between changes in MBT parameters and changes in other liver related parameters

Repeat MBT results (cPDR₃₀, PDR_{peak} or other breath test parameters) and their changes in subjects with and without treatment (BMS-986036) for nonalcoholic steatohepatitis (NASH) at Day 1, Week 24 and Week 48 (or Early Termination visits) will be compared and tested for correlation to baseline, as well as repeat results (change from baseline), for the following measurements:

- a. Biopsy based Fibrosis and/or NAS score
- b. Liver stiffness as measured by MRE
- c. PDFF as measured by MRI
- d. Serum Pro-C3 results
- e. Liver elastography by Fibroscan (in cohort 2 only)
- f. MELD scores (in cohort 2 only)
- g. CTP scores (in cohort 2 only)

Linear Regression will be applied in order to test for significance of the correlations between MBT and the liver measurements listed above.

Changes in MBT are measured as the difference between baseline and each of the MBT visits as well as the change in measurements between two subsequent visits in each of the two treatment groups.

Meridian Bioscience Israel Ltd.	Last update: May 05, 2021
SAP for Protocol BMS-EX-0118: Companion protocol for the ¹³C-Methacetin Breath Test (MBT) for use in Bristol-Myers Squibb phase 2b studies for BMS-986036 (PEG-FGF21), under Protocols MB130-068 and MB130-069	Document Version: 1.0
Document Nº: CSD00114	Page 18 of 21

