8.5 Site Poolability

Primary efficacy analysis will be reported for each cohort separately as well as for each site/group of sites (see next section) separately.

For sites with less than 10 subjects, the following pooling of sites method will be applied for each cohort separately: Sites will be sorted from smallest to largest based on the number of randomized subjects with valid baseline MBT results. The smallest site will be pooled with the second smallest, and if necessary with the next sites in line until the site group reaches 10 subjects or more. The site value for those sites will be assigned "Site Group 1". Then the next site in line, if lower than 10 subjects, will be pooled with the sites after it until the site group reaches at least 10, and so forth until all sites or site groups have at least 10 subjects. Furthermore, site by MBT dichotomy interaction will be added to the Linear and Cox regression models as a covariate to test for site effect on the exploratory endpoints.

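### SAP 8.4.2.1 asks for an exact confidence interval that a standard Cox fit does not give and selects the arm term by its p-value; SAP 8.5 should label the site interaction as a supplementary check

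*SAP*

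**What the plan says.** SAP 8.4.2.1 serves the first secondary objective, the prognostic value of the breath test. PDRpeak of 20 %/h or less is high risk and anything above is lesser risk. This class enters a "Cox proportional hazards regression model with site and randomized arm as covariates". The hazard ratio is wanted "for classifying Subjects into risk groups for clinical deterioration with respective exact two-sided 95% confidence intervals", in the placebo and treatment arms.

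The arm term depends on a preliminary fit. If its p-value exceeds 0.05, "then this factor will not be a covariate for the main analysis to be performed"; otherwise it stays. On output, "The model summary will include the number of subjects in the model, and a table with each covariate in a separate line", with coefficient, hazard ratio, 95% interval and p-value.

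SAP 8.5 pools small sites "until all sites or site groups have at least 10 subjects". It then crosses MBT class with site: "MBT dichotomy interaction will be added to the Linear and Cox regression models as a covariate to test for site effect on the exploratory endpoints". The linear models are those of SAP 8.4.2.2: "Linear Regression will be applied in order to test for significance of the correlations between MBT and the liver measurements listed above".

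SAP 4.1 says that the number of subjects with valid baseline and post-treatment breath tests, "across both BMS studies, is expected to be lower than 80". SAP 6.1 makes every analysis descriptive, with nominal p-values.

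**The concern.** Four things need attention in the reported hazard ratio.

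1. **Interval.** The usual Cox limits are Wald or profile-likelihood limits, both large-sample. The SAP asks for exact limits and names no method. The word seems carried over from Protocol 9.2.2, which allowed Cox or logistic regression; the SAP keeps only Cox.
2. **Sparse events.** If all events fall in one MBT class, the unpenalised estimate is zero or infinite. No rule covers this.
3. **Arm.** The final model depends on a p-value from the same data.
4. **Interaction.** SAP 8.5 does not say that the interaction model is separate from the one that supplies the reported hazard ratio. Its wording is also loose: it refers to exploratory endpoints, while the SAP's only Cox model serves a secondary objective, and the linear models in 8.4.2.2 name neither site nor an MBT dichotomy.

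At stake are the hazard ratio and interval for one secondary objective.

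**Working it through.** The plan gives no event count, expected hazard ratio or power for this analysis, so there is no figure to reproduce.

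**Inputs from the SAP.** N below 80, so 79 is used (4.1); site groups of at least 10 (8.5); four arms (section 4). **Assumptions.** 4, 7.5 or 14 events; share at high risk s = 0.35; hazard ratio 2. The Cox model needs only a baseline test, so its denominator could exceed 79.

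**Main-effects model.** Let pl and ph be the event risks in the lesser- and high-risk classes, with ph = 1 − (1 − pl)² and s·ph + (1 − s)·pl = events/79. The chance that at least one class has no event is A + B − C, where A = (1 − s·ph)^79, B = (1 − (1 − s)·pl)^79 and C = (1 − s·ph − (1 − s)·pl)^79.

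| Events | pl | ph | A | B | C | A + B − C | Simulated |
|---|---|---|---|---|---|---|---|
| 4 | 0.0379 | 0.0743 | 0.1247 | 0.1395 | 0.0165 | 0.248 | 0.245–0.260 |
| 7.5 | 0.0717 | 0.1382 | 0.0199 | 0.0231 | 0.0004 | 0.043 | 0.039–0.040 |
| 14 | 0.1361 | 0.2536 | 0.0007 | 0.0007 | 0.0000 | 0.001 | 0.002–0.004 |

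The last column is the share of unpenalised fits without a finite MBT hazard ratio. It comes from 1,000 simulated datasets per setting: 336 days, exponential times, 20% early censoring, 2, 4 or 7 equal site groups, datasets without events excluded. Repeating the formula with ph = 1 − (1 − pl)^HR for s of 0.20, 0.35 and 0.50 crossed with hazard ratios of 1, 2 and 4 gives about 25% to 47% at 4 events, 4% to 22% at 7.5 and 0.1% to 6% at 14.

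**Firth fit of MBT class plus site groups** (600 datasets per setting). The estimate and both profile limits were always finite, and coverage was 92.7% to 96.7%. The median ratio of upper to lower limit was about 64 to 79 at 4 events, 19 to 22 at 7.5 and 8.5 to 10 at 14.

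**Arm rule.** With no true arm effect, the rule kept arm in 4.5% to 11.5% of runs. A separate simulation (N = 79, no site term, MBT hazard ratio 3, event risk 20% to 40% before any arm effect, active-arm hazard ratios 1.0 to 0.3) gave 95% interval coverage of 95.7% to 97.6% with the rule, 95.5% to 97.4% with arm always in and 96.2% to 98.3% with arm always out.

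**Interaction, literal reading only.** At most 7 groups of 10 fit into 79. With 7 groups and arm kept, the model has 1 + 6 + 3 = 10 parameters without the interaction and 10 + 6 = 16 with it. Under reference coding, the MBT line then describes one group of 79/k subjects. Replacing the exponent 79 by 79/k gives the chance that this line is not finite:

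| Events | k = 2 | k = 4 | k = 7 |
|---|---|---|---|
| 4 | 0.598 | 0.847 | 0.941 |
| 7.5 | 0.274 | 0.626 | 0.831 |
| 14 | 0.051 | 0.299 | 0.591 |

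These values depend on the assumptions: with s = 0.20 and hazard ratio 1 together, the 14-event, 4-group value rises from 0.299 to 0.518.

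**The case against.** The strongest answer concerns the interaction. SAP 8.4.2.1 lists the covariates of its Cox model, refers to a main analysis and includes no interaction. SAP 8.5 stands under site poolability and gives the term a testing purpose. That answer stands. A reader might infer that the plan will report the interaction model and so will usually have no usable hazard ratio. The documents do not support this, and the second table does not describe the likely report.

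Three further inferences also fail:

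- **The arm term is left open.** It is not. The rule is complete, with a stated threshold and both outcomes. It can be criticised only as a data-dependent choice, and the coverage figures show no harm. The Day 1 test also precedes the first dose.
- **It is unclear which cohorts contribute events.** Protocol 7.7.2 speaks of cohort 2, but SAP 3.1.2 puts this objective on the combined population and on each cohort separately, SAP 3.2.2 lists the outcome outside the cohort 2 measures, and SAP section 2 says that the SAP prevails.
- **These choices must be made after the data are seen.** SAP section 2 provides for amendment before the sponsor accesses the data.

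It is also fair to say that Firth penalisation does not create information and that the plan already has a Kaplan-Meier plot, a log-rank p-value and a crosstab, which work with few events. Those outputs limit the damage, but they do not supply the hazard ratio and interval that the SAP asks for.

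**Conclusion.** The point holds as a minor correction to the Cox hazard ratio and its interval. The request for an exact interval cannot be met by a standard Cox fit. The unpenalised main-effects estimate has a material chance of being zero or infinite if events are very few: about one trial in four at 4 events, 4% at 7.5 and under 1% at 14. These rates rest on 79 subjects, a hazard ratio of 2 and 35% at high risk; the event counts are assumptions because the documents give none. Selecting arm by its p-value is a weakness of pre-specification without demonstrated bias. For SAP 8.5, the conclusion is only that the supplementary role of the interaction should be written down.

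**What to change.** **SAP 8.4.2.1.** State that the MBT hazard ratio is reported from the model with MBT class and site groups, without the interaction, fitted with Firth penalisation. Replace the exact interval by a profile-likelihood 95% interval. Decide the arm term in advance: for example, leave it out and show one active-versus-placebo term as a sensitivity analysis. Say whether the same method serves the hazard ratios requested by arm, where events will be fewer still.

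**SAP 8.5.** Label the Cox interaction as a supplementary poolability check that does not supply the reported hazard ratio. Name the analyses meant by exploratory endpoints, and say how the term enters the linear models.

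**Cost.** A few sentences, before data access, and standard software. The interval will be finite but still very wide at low event counts, as the Firth results above show, and should be presented in that light.

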8.6 Safety Analyses

The adverse events possibly or probably related to Methacetin and/or the BreathID® MCS device will be presented along with a two sided 95% exact binomial confidence interval. The analysis of all adverse events will include incidence tables and will include analyses by severity, relationship to device or drug and baseline variables.

No inferential statistical testing will be performed for safety variables.

Meridian Bioscience Israel Ltd.	Last update: May 05, 2021
SAP for Protocol BMS-EX-0118: Companion protocol for the ¹³C-Methacetin Breath Test (MBT) for use in Bristol-Myers Squibb phase 2b studies for BMS-986036 (PEG-FGF21), under Protocols MB130-068 and MB130-069	Document Version: 1.0
Document N°: CSD00114	Page 19 of 21

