9.2.3 Safety endpoints measure

The cumulative incidence of adverse events, serious adverse events (SAE), suspected unexpected serious adverse reactions (SUSAR) and unanticipated adverse device effects (UADE) possibly or probably related to the use of the BreathID MCS device and its substrate or related to the procedure, will be collected and reported.

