12 SAFETY CONSIDERATIONS

All adverse events (AE), serious adverse events (SAE), suspected unexpected serious adverse reactions (SUSAR) and unanticipated adverse device effects (UADE) possibly or probably related to the use of the MBT product or related to the MBT procedure will be collected and reported according to local regulations.

Safety assessments of the BMS study drug (BMS-986036) will be performed as described in BMS protocols MB130-068 and MB130-069.

| | |
|---|---|
| Exalenz Bioscience Ltd. | Last update: February 20, 2018 |
| Study Title: Companion protocol for the ¹³C-Methacetin Breath Test (MBT) for use in Bristol-Myers Squibb phase 2b studies for BMS-986036 (PEG-FGF21), under Protocols MB130-068 and MB130-069 | Protocol: BMS-EX-0118 Version: 1.0 |
| Document No: CSP000002 | Page 37 of 38 |

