5. To assess the ability of changes in the MBT to reflect changes in Serum Pro-C3, where available, at Week 24 and Week 48 of treatment (or Early Termination), compared to baseline Pro-C3 from the screening visit.

The same assessments for each study cohort independently will be reported.

The following additional objectives are applicable for cohort 2 only:

1. To assess the ability of changes in the MBT to reflect changes in liver stiffness as measured by “Fibroscan” elastography, where available, at the Week 48 visit (or earlier if there was an Early Termination) compared to the screening visit.
2. To assess the ability of changes in the MBT to reflect changes in the Model for End-stage Liver Disease (MELD) score, where available, at Week 24 and Week 48 visits compared to study Day 1.
3. To assess the ability of changes in the MBT to reflect changes in the Child-Turcotte-Pugh Scoring (CTP) score, where available, at Week 24 and Week 48 (or Early Termination) compared to study Day 1.

Meridian Bioscience Israel Ltd.	Last update: May 05, 2021 Document Version: 1.0
SAP for Protocol BMS-EX-0118: Companion protocol for the ¹³C-Methacetin Breath Test (MBT) for use in Bristol-Myers Squibb phase 2b studies for BMS-986036 (PEG-FGF21), under Protocols MB130-068 and MB130-069	
Document Nº: CSD00114	Page 10 of 21

3.1.3 *Exploratory Objective*

- To assess the ability of the MBT to monitor patient status in comparison to other available measures, such as Liver Fibrosis stage, NAS, MELD, CTP, PDFF, Liver Stiffness, Serum Biomarker or Pro-C3.

3.1.4 *Safety Objective*

Evaluation of safety related to the MBT.

3.2 *Study Endpoints*

3.2.1 *Primary Endpoint*

The MBT's ability to measure the effect of BMS-986036 treatment on the metabolic capacity of the liver at Week 24 and Week 48 visits during the Double-Blind Treatment Period, as compared to changes in placebo treated subjects.

3.2.2 *Secondary Endpoints*

In order to assess the correlation of changes in MBT with changes in other measures of liver disease, the following endpoint measures will be collected, where available:

For all study cohorts: MBT results for each MBT visit (Day 1, Week 24, Week 48, or Early Termination visits) as well as changes in MBT results (cPDR₃₀, PDR_{peak} or other breath test parameters).

The other measures of liver disease that will also be collected in this study are as follows:

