7 ANALYSIS SETS

7.1 *Safety Analysis Set (SA)*

The Safety Analysis set will include all subjects enrolled under BMS' MB130-068 and MB130-069 studies that initiated at least one MBT (had taken the ¹³C-Methacetin solution), even if the MBT was not completed or the result was not valid.

7.2 *Efficacy Analysis Set (EA)*

The Efficacy Analysis set will include all subjects enrolled under BMS' MB130-068 and MB130-069 studies who have successfully performed the MBT test and did not have any major protocol deviations for the current study.

7.3 *Modified Efficacy Analysis Set (mEA)*

The modified Efficacy Analysis set will include all subjects enrolled under BMS' MB130-068 and MB130-069 studies who have successfully performed the MBT test. Visit specific major protocol deviation will be excluded, while keeping subjects in this analysis set for other valid visits.

Safety analyses will be performed on the SA set and efficacy analyses on the mEA set. Sensitivity analysis will be performed on the SA (corresponding to ITT) and EA set.

Meridian Bioscience Israel Ltd.	Last update: May 05, 2021
SAP for Protocol BMS-EX-0118: Companion protocol for the ¹³C-Methacetin Breath Test (MBT) for use in Bristol-Myers Squibb phase 2b studies for BMS-986036 (PEG-FGF21), under Protocols MB130-068 and MB130-069	Document Version: 1.0
Document Nº: CSD00114	Page 15 of 21

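### The related-event rate in SAP 8.6 (and Protocol 9.6.4) omits events attributed only to the MBT procedure, which Protocol 9.2.3 makes part of the safety endpoint

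*SAP*

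**What the plan says.** Protocol 9.2.3 sets the safety endpoint as the cumulative incidence of AEs, SAEs, SUSARs and UADEs "possibly or probably related to the use of the BreathID MCS device and its substrate or related to the procedure, will be collected and reported". Protocol section 12 uses the same two-part attribution for collection and reporting: events "possibly or probably related to the use of the MBT product or related to the MBT procedure will be collected and reported", subject to local regulations.

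The analysis sections are narrower. SAP 8.6 begins: "The adverse events possibly or probably related to Methacetin and/or the BreathID® MCS device will be presented". The same sentence gives these events, and no others, an exact 95% interval. It then says that all adverse events will have incidence tables, and that this analysis "will include analyses by severity, relationship to device or drug and baseline variables". Protocol 9.6.4 has the same wording.

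The SAP lists no safety endpoint in its section 3.2. Its safety objective (3.1.4) is "Evaluation of safety related to the MBT". The safety analysis set in SAP 7.1 is everyone who "initiated at least one MBT (had taken the ¹³C-Methacetin solution"), even if the test was incomplete or invalid.

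**The concern.** The endpoint has two routes to being MBT-related: product (device and substrate) and procedure. The only related-event estimate that carries an interval covers the first route alone, and the relationship breakdown has no procedure category. An analyst who follows SAP 8.6 literally would leave out of the related-event rate any subject whose only MBT-related event was attributed to the procedure.

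The test has steps to which such an event could be attributed. Protocol 10.2 describes fasting, withheld medicines and up to 85 minutes seated while breath is collected. It also says that giving fluids may, rarely, cause vomiting, and it ties that event to the fluids rather than to methacetin.

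The stakes are modest but real. Safety of the MBT is a stated objective, and both documents say that the data may be used for future submissions.

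**Working it through.** **Step 1: compare the passages.**

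| Place | Attribution named | Output |
|---|---|---|
| Protocol 9.2.3 | Device and substrate, or procedure | Cumulative incidence of AEs, SAEs, SUSARs, UADEs |
| Protocol 12 | MBT product, or MBT procedure | Collected and reported |
| Protocol 9.6.4 | Methacetin and/or device | Related AEs with exact 95% CI |
| SAP 8.6, first sentence | Methacetin and/or device | Related AEs with exact 95% CI |
| SAP 8.6, second sentence | All AEs; relationship split by device or drug | Incidence tables, no CI stated |

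The endpoint and its analysis therefore already disagree inside the protocol (9.2.3 against 9.6.4), and the SAP carries the narrower wording forward. SAEs, SUSARs and UADEs are in the SAP abbreviation list, but no SAP analysis names them.

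**Step 2: follow one event through the plan.** Take a subject in the safety set whose only MBT-related event is attributed to the procedure alone.
- Endpoint in 9.2.3: counted.
- All-AE incidence tables in SAP 8.6: counted.
- Related-event rate with CI in SAP 8.6: not counted.
- Relationship breakdown: no category identifies it.

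Adding such subjects to the numerator with the denominator fixed can only raise the rate or leave it unchanged. Any discrepancy from the endpoint is therefore downward.

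**Step 3: size.** The documents state no safety rate, expected event count or safety-set size, so there is no plan figure to reproduce. What follows is an illustration with assumed inputs. I take the binomial unit as a subject with at least one related event, which SAP 8.6 does not spell out.

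- Assumed N: 50, 80 and 250. The SAP expects fewer than 80 subjects with valid baseline and post-treatment MBTs, which is a different and more restricted group than the safety set. The initial plan was for up to 250.
- Assumed counts: x = 0 as reported, against x = 2 if two procedure-only subjects were included.
- Clopper-Pearson limits: lower = the 0.025 quantile of Beta(x, N − x + 1), which is 0 when x = 0; upper = the 0.975 quantile of Beta(x + 1, N − x). For x = 0 the upper limit reduces to 1 − 0.025^(1/N). At N = 80 this is 1 − 0.025^(1/80) = 4.51%.

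| N (assumed) | x = 0: rate (95% CI) | x = 2: rate (95% CI) | Ratio of upper limits |
|---|---|---|---|
| 50 | 0% (0 to 7.11%) | 4.0% (0.49 to 13.71%) | 13.71/7.11 = 1.93 |
| 80 | 0% (0 to 4.51%) | 2.5% (0.30 to 8.74%) | 8.74/4.51 = 1.94 |
| 250 | 0% (0 to 1.46%) | 0.8% (0.10 to 2.86%) | 2.86/1.46 = 1.96 |

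With sparse events, two omitted subjects roughly double the upper limit at any of these sizes.

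**The case against.** The best defence is that little is lost. All adverse events are tabulated, with a breakdown by severity, and 9.2.3 asks for cumulative incidence, not for an interval. On that view a procedure-only event loses a confidence interval and a label, not its place in the report. This stands as far as it goes, and it rules out the stronger reading that procedure-related events disappear from the safety analysis. It does not answer the mismatch. The endpoint is the incidence of related events, and the all-AE tables give no means of recovering the procedure-related part.

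A reader might also infer that the SAP departed from the protocol. It did not: Protocol 9.6.4 has the same wording, so the SAP's precedence clause adds little here. The conflict is between 9.2.3 and 9.6.4.

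Attribution may overlap. The nasal cannula attaches to the device and comes in the test kit, so its events might be coded to the device. Vomiting after drinking might be coded to the substrate. The documents give no coding rule. The loss is therefore certain only for events coded solely to the procedure, and that class may be empty.

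Three further inferences are not supported:
- That the safety set is defective because it requires ingestion. SAP 7.1 expressly keeps incomplete and invalid tests, and both listed reasons for terminating a test concern events after ingestion. A subject would be missed only by never ingesting at any visit.
- That each of SAEs, SUSARs and UADEs needs its own interval. Protocol 9.2.3 asks for incidence only.
- That the protocol counts effects of the pre-test restrictions as procedure-related. Neither 9.2.3 nor section 12 says so.

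Finally, this is a descriptive feasibility study, and Protocol 7.4 expects no serious adverse events related to the breath test. That limits the weight of the point but does not remove it.

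**Conclusion.** The point holds in a limited form. Read literally, SAP 8.6 and Protocol 9.6.4 estimate a related-event rate narrower than the endpoint in Protocol 9.2.3, and the difference can run only towards understatement. It affects the related-event rate and the relationship breakdown, not the all-AE tables.

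The actual size is unknown. The illustrated shifts in the upper limit (7.1% to 13.7% at N=50, 4.5% to 8.7% at N=80, 1.5% to 2.9% at N=250) rest on an assumed N, on assumed counts of none against two, and on those two events being coded to the procedure alone. They show sensitivity and do not predict a result. The tempting conclusion that the test's safety rate will be materially wrong goes beyond the documents, which give no evidence that any such event occurred. A correction is still worthwhile, because the wording conflict is plain and inexpensive to remove.

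**What to change.** In SAP 8.6, and for consistency in Protocol 9.6.4, define the related-event numerator as AEs possibly or probably related to methacetin, the BreathID MCS device or the MBT procedure. Keep the exact 95% interval. Add procedure as a relationship category in the AE tables where the collected data allow. Report the incidence of related SAEs, SUSARs and UADEs, as 9.2.3 states.

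The SAP is dated May 2021, expects the databases between July and November 2021, and allows amendment before the data are accessed, so the change fits its own timetable. MBT testing was already complete by then, and the documents do not show whether the eCRF recorded relationship to the procedure. If it did not, the report should say that the procedure component cannot be separated.

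The cost is a few words, minor extra tabulation, and possibly a slightly less favourable related-event rate.
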